All investigators and sub-investigators will receive training on the above techniques prior to site initiation. Training will either be in-person or via video teleconference. Additionally, each site must confirm that they stock the Raptor, VacLok syringe, and Carrier navigation catheter prior to site initiation.

Objective and endpoints

Study objective

The object of this study is to compare the efficacy and safety of the Plunger technique vs static aspiration for direct aspiration thrombectomy using the Raptor aspiration catheter.

Primary effectiveness endpoint

The primary endpoint is the first pass effect (FPE), defined as TICI 2c or 3 after the first attempt of direct aspiration thrombectomy, as determined by core lab assessment (see p. 16)

Primary safety endpoint

The primary safety endpoint is the rate of symptomatic intracranial hemorrhage (sICH) at 24 hours, as defined by 1) new intracranial hemorrhage on CT and 2) neurologic deterioration associated with worsening NIHSS by 4 or more points.

Secondary endpoints

- Overall rate of TICI 2b or 3 recanalization with Plunger technique vs. static aspiration vs. rescue therapy. At least one thrombectomy attempt with the assigned technique will be made prior to rescue treatment with a stent-retriever or other device if needed.
- Functional outcome at 90 days based on modified Rankin scale (mRS) assessment. All patients will be contacted *by phone* at 90 days to assess their functional status.

- Rate of successful navigation of aspiration catheter to clot. This will be reported by the site investigator. If the aspiration catheter cannot be navigated to the clot then rescue treatment with a stent-retriever may be used.
- Rate of rescue treatment with stent-retrievers. This rescue therapy will be employed after **at least** one attempt with aspiration thrombectomy, or if the Raptor cannot be successfully navigated to the clot.
- Rate of complete clot ingestion. Sites will report if the clot is completely ingested through the Raptor and into the syringe, or if it is partially ingested in the tip of the Raptor.
- Recanalization rates with the two different sizes of Raptor: analyses will compare recanalization of the 0.071" vs. 0.074" sizes of Raptor.

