- Rate of recanalization by clot density on CT (hyperdense vs isodense). There is evidence that hyperdense clot contains a higher fraction of red blood cells, is softer, and is more readily removed with thrombectomy devices. This has not been assessed in aspiration thrombectomy.

Risk Assessment

- This study poses no more than minimal risk to participants. All subjects will undergo a standard mechanical thrombectomy procedure, with the only difference being the method of aspiration; either static or cyclic (Plunger) technique. Both techniques are widely used in clinical practice, are considered standard of care, and have comparable safety profiles. No investigational devices or procedures will be used. As such, participation in the study does not expose subjects to risks beyond those encountered in routine clinical care.

Investigational plan

Trial design

The Plunger trial is a prospective, multicenter, randomized, controlled trial of the Plunger technique vs. static manual direct aspiration thrombectomy to assess recanalization efficacy for treatment of acute large vessel occlusion stroke. Participants will have a large vessel occlusion in the anterior circulation of the terminal ICA or M1 segment of the MCA.

Ethical Considerations and Informed consent

This study compares two suction techniques: static aspiration and the cyclic aspiration (plunger technique) both of which are standard practices in mechanical thrombectomy. These techniques are routinely employed by physicians based on individual preference and training. All procedures involved are part of routine clinical care and utilize FDA-cleared devices (e.g., Raptor catheters and 60cc VacLok syringes). No investigational devices or experimental procedures are introduced. Importantly, both techniques have similar/identical risk profiles, as they are commonly used in clinical practice and do not introduce additional risks beyond those encountered in standard stroke treatment. Therefore, this study meets the definition of minimal risk research under federal regulations.

Informed consent process:

The patient consent process will be conducted using a REDCap-based electronic consent form. The consent form has been developed in REDCap, a secure, web-based, HIPAA-compliant, data collection platform with a user management system allowing project owners to grant and control varying levels of access to data collection instruments and data (e.g. read only, de-identified-only data views) for other users.

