A participant will be considered lost to follow-up for the secondary end-point, mRS, if he or she is unable to be contacted by the study site staff, either via telephone or an in-person meeting at 90-days after randomization. When all reasonable attempts to locate the subject have been exhausted, the subject will be considered lost to follow-up and their data will be excluded from the data analysis from the time of last contact onward. All data collected prior to last contact will be included in data analysis.

Statistical analysis

Sample size calculation

The true rate of successful FPE with aspiration thrombectomy can be estimated based on several prior studies. The COMPASS trial reported an 83% rate of TICI 2b or 3 after the first attempt with aspiration thrombectomy [4]. Similarly, Kang et al reported TICI 2b or 3 in 82% of patients after the first pass with aspiration thrombectomy [8], but that rate dropped to 19% when limiting the definition of successful FPE to TICI 2c or 3 [8]. Similarly, the ETIS investigators reported a 24% rate of TICI 3 FPE with the Sofia catheter [9]. Synthesizing these results, we estimate the predicted FPE (TICI 2c or 3) rate of static aspiration thrombectomy to be 25%.

While it is difficult to predict the treatment effect of the Plunger technique, our experience is that there is significantly more total clot ingestion with this technique. Total clot ingestion would be expected to particularly impact the TICI 2c/3 rate of FPE. Therefore, we estimate that the Plunger technique may increase FPE rate by 15% over static aspiration (predicted Plunger FPE of 40%).

A minimum sample size of 462 would be required to detect a difference of 15% between these two groups with 90% power at alpha of 0.05. Given that the actual FPE rates are difficult to estimate and accounting for inability to access the lesion with the Raptor and missing data, we plan for a total minimum sample size of 500.

Population for analysis

A modified intention-to-treat (mITT) analysis will be employed, wherein all subjects for whom navigation of the Raptor to the clot failed will be excluded from the subsequent ITT analyses. This is because those subjects will not be treated by either of the techniques being studied in this trial. Once navigation failures are excluded, the remainder of the population will be compared based on assigned treatment technique per randomization.

Analysis of primary effectiveness endpoint

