The primary endpoint is the first pass effect (FPE), defined as TICI 2c or 3 after the first attempt of direct aspiration thrombectomy, as determined by core lab assessment. The rate of successful FPE will be compared between the Plunger group and the static aspiration group per the mITT population as above.

Null hypothesis: the rate of successful FPE is not different between static and plunger aspiration. The rate of FPE will be compared between the two groups by chi-square analysis. If there is a significant difference between the two, then the null hypothesis will be rejected.

Analysis of primary safety endpoint

The primary safety endpoint is the rate of sICH at 24 hours compared between the static and Plunger aspiration groups. A chi-square test will assess for differences in rate of sICH between the two treatment groups in the mITT population. Secondary analyses will account for ASPECTs score and time to treatment between the two groups.

Analysis of secondary endpoints

Overall rate of TICI 2b or 3 recanalization with Plunger vs. static aspiration will also be compared using chi-square analysis on the mITT population.

For the following additional binomial secondary efficacy endpoints, treatment groups will be compared using logistic regression models as appropriate:

- Rate of successful navigation of aspiration catheter to clot
- Rate of rescue treatment with stent-retrievers
- Rate of complete clot ingestion
- Rate of recanalization by clot density on CT (hyperdense vs isodense)

The 90-day functional outcomes, including mRS and PROMIS-10, will be compared between the two groups using ordinal shift analysis.

Randomization

Patients will be randomized (1:1; permuted block randomization) once the decision is made for patient to go for thrombectomy using the REDCap randomization tool.

Adverse events

Throughout the course of the clinical investigation, all adverse events will be recorded on the applicable Adverse Event CRF. The date of onset, date of resolution, severity, and action taken will be evaluated by the Investigator. The relationship to the technique or device, relationship to the procedure, and clinical significance will be evaluated. The neurological outcomes and adverse events will be reported.

Adverse Event Classification and Definitions

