Any amendment or modification to the clinical protocol must be sent to the IRB. The IRB must also be informed of any event likely to affect the safety of subjects or the conduct of the study. If the IRB imposes any additional requirements (e.g. safety reports, progress reports etc.), this will be followed, if appropriate.

A Data and Safety Monitoring Board (DSMB) will oversee participant safety and data integrity throughout the study. DSMB members will include experts in neuro intervention, biostatistics, and clinical trial execution. Their responsibilities will include:

- Reviewing safety and efficacy data at regular intervals
- Advising on study continuation, modification, or termination

Electronic Data Capture and Monitoring

VUMC will oversee data management using Redcap, a secure electronic data capture system. The system includes built-in checks to support data accuracy and protocol compliance. The Project Manager will conduct monthly data reviews to identify and resolve discrepancies. All study personnel will be trained in data entry procedures and Good Clinical Practice (GCP) standards.

The Project Manager (PM) will conduct monthly data reviews to identify outliers, inconsistencies, and missing information. Discrepancies will be addressed through open queries in REDCap and resolved in a timely manner to maintain data quality.

Staff Training: All study personnel involved in data entry and protocol implementation will receive training on the protocol, REDCap use, and Good Clinical Practice (GCP) standards.

Protocol Adherence Monitoring: Compliance will be assessed through monthly check-ins and quarterly oversight meetings. Any deviations will be documented, reviewed, and reported to the IRB as required.

References

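### The primary safety analysis is a chi-square test of difference in a trial sized only for first pass effect, so a non-significant sICH result would not show how large an excess is excluded

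*Protocol*

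**What the plan says.** **Endpoint.** Under Primary safety endpoint: "The primary safety endpoint is the rate of symptomatic intracranial hemorrhage (sICH) at 24 hours". An event requires new hemorrhage on CT and a worsening of at least 4 NIHSS points. The study objective is to compare both the efficacy and the safety of the two techniques.

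**Analysis.** Under Analysis of primary safety endpoint: "A chi-square test will assess for differences in rate of sICH between the two treatment groups in the mITT population". The next sentence adds: "Secondary analyses will account for ASPECTs score and time to treatment between the two groups". No effect estimate, interval, margin or rule for reading a non-significant result is attached.

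**Size.** Under Sample size calculation: "A minimum sample size of 462 would be required to detect a difference of 15% between these two groups with 90% power at alpha of" (the level given is 0.05). That difference is in FPE, 25% against 40%. The section then says "we plan for a total minimum sample size of 500". It mentions neither sICH nor an expected sICH rate.

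**Oversight.** A Data and Safety Monitoring Board's duties include "Reviewing safety and efficacy data at regular intervals".

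**Statements on risk.** Risk Assessment says both techniques "are considered standard of care, and have comparable safety profiles". Ethical Considerations and Informed consent says "both techniques have similar/identical risk profiles, as they are commonly used in clinical practice". Both serve to justify the minimal-risk classification.

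**The concern.** In a safety comparison the reassuring result is a failure to reject, and low power makes that result more likely whatever the truth is. A test of difference answers whether the arms can be told apart. The question of interest is how much extra sICH with the Plunger technique the data still allow, and a p-value alone does not answer it.

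The trial was sized for a 15-point difference in a common outcome. If sICH is uncommon, the same number of patients gives limited power for a clinically important ratio. The likely report would then be no significant difference, set beside a protocol that already describes the two techniques as similar in risk. A reader could take the one as confirming the other. The safety half of the objective would rest on a statement that does not bound the harm.

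**Working it through.** **Inputs**
- Patients per arm: 500/2 = 250 (planned total) and 462/2 = 231 (stated minimum), with 1:1 allocation. The mITT population excludes navigation failures, so fewer than 250 per arm may be analysed.
- Two-sided alpha 0.05. The protocol gives 0.05; two-sided is assumed.
- Static-arm sICH rate p: not in the protocol. Assumed range 2% to 6%.
- Alternative: a doubling, q = 2p. This is an illustrative choice.

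**The plan's own figure.** No power or sample size is stated for sICH, so there is nothing to reproduce for safety. For FPE, with the mean rate 0.325:

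n per arm = [(1.96·√(2·0.325·0.675) + 1.2816·√(0.25·0.75 + 0.40·0.60)) / 0.15]² = [(1.298 + 0.838)/0.15]² ≈ 202.8, rounded up to 203.

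That is 406 in total (432 with continuity correction), not 462. The stated figure is larger than needed, so the discrepancy is conservative. It is a separate matter and does not affect this point.

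**Power for sICH.** With m = (p + q)/2,

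power = Φ{ [ (q − p)·√n − 1.96·√(2m(1 − m)) ] / √( p(1 − p) + q(1 − q) ) }.

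Example, 5% against 10% with 250 per arm: m = 0.075; (q − p)√n = 0.7906; 1.96·√0.13875 = 0.7301; √0.1375 = 0.3708. So z = (0.7906 − 0.7301)/0.3708 ≈ 0.163 and power ≈ 56%.

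| Assumed static rate → doubled | Power, 231 per arm | Power, 250 per arm | Missed |
|---|---|---|---|
| 2% → 4% | 24% | 26% | 74–76% |
| 3% → 6% | 34% | 37% | 63–66% |
| 4% → 8% | 44% | 47% | 53–56% |
| 5% → 10% | 53% | 56% | 44–47% |
| 6% → 12% | 62% | 65% | 35–38% |

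Exact binomial enumeration of the uncorrected test agrees within about 1 point. A Yates correction lowers power further, for example to 50% at 5% → 10% with 250 per arm. Power of 80% for a doubling needs a static rate of about 8.2% (250 per arm) or 8.8% (231 per arm).

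**What an interval would show.** With equal true rates, the approximate 95% half-width for the difference is 1.96·√(2p(1 − p)/n).
- At 2%: 2.5 points (250 per arm) or 2.6 points (231 per arm).
- At 6%: 4.2 points (250 per arm) or 4.3 points (231 per arm).

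**Illustration.** Take 10 static and 20 Plunger events with 250 per arm, an observed 4% against 8%. The uncorrected chi-square is 500·(20·240 − 10·230)² / (30·470·250·250) = 3.55, p = 0.06. The planned test reports no significant difference. A score interval for the excess runs from about −0.2 to 8.4 points. It shows that an excess of 8 points is still compatible with the data.

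**The case against.** Several objections have force.

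- **The protocol does not plan to claim equivalence.** A reader might infer that it will use the chi-square result to prove comparable safety. The text does not support this. The statements on similar risk are background premises for the minimal-risk classification, the objective names no equivalence or non-inferiority aim, and the analysis section speaks only of assessing differences. What stands is narrower: a non-significant result should not be taken to confirm those premises.
- **The chi-square test is not the only look at safety.** Analyses accounting for ASPECTS and time to treatment are planned, the safety board reviews data, and narrative reports of perforation, dissection and death at 24 hours are required. This is correct. As written, though, none of these supplies an interval, a margin or a rule for reading a non-significant result.
- **The sICH rate is an assumption.** It might be said that a doubling would be missed about half the time. That holds only near a static rate of 4% to 5%; the range is the defensible statement.
- **Sparse counts.** A reader might add that the chi-square approximation fails. Expected events fall to about 5 per arm only near 2% (4.6 to 5.0), and exact enumeration shows little consequence, so no weight is placed on this.
- **An interval may be in the statistical analysis plan,** which is not shown, and naming a chi-square test does not exclude one. That is fair. The point rests on what the protocol fixes as the primary safety analysis, which is a test of difference.
- **The fix adds no power.** True. It makes the imprecision visible.

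**Conclusion.** The point holds in a limited form. The protocol fixes a test of difference as the main analysis of its primary safety endpoint in a trial sized only for FPE. For an assumed static-arm sICH rate of 2% to 6% and 231 to 250 analysed per arm, that test would miss a true doubling about 35% to 76% of the time. Non-significance therefore cannot show how large an excess is excluded. The figures depend on the assumed rate, on a doubling as the alternative, on a two-sided 0.05 level and on the uncorrected test; power would be lower with fewer patients analysed or with a continuity correction.

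The efficacy analysis is unaffected. This is a worthwhile, low-cost improvement to the safety analysis, not an error that threatens the trial.

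**What to change.** In Analysis of primary safety endpoint, replace the first analysis sentence with wording such as:

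> The primary safety analysis is the risk difference in sICH at 24 hours (Plunger minus static) in the mITT population, with a two-sided 95% Miettinen-Nurminen confidence interval. Safety will be interpreted from this interval, in particular its upper limit. A chi-square test will be reported as supportive. A non-significant result will not be read as evidence of equal safety.

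The analyses accounting for ASPECTS and time to treatment can stay as they are.

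**Cost.** Wording only: no extra patients, no new data, no margin and no change to patient management. The downside is that the safety conclusion becomes a stated range. With equal rates it would be about ±2.5 points at 2% to ±4.3 points at 6%, somewhat wider with a score interval when events are few. That is less favourable than a bare statement of no difference.

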Patients with a large vessel occlusion who are clinically appropriate for thrombectomy will be screened for participation. Subjects who meet selection criteria below will be enrolled. Note that there are no parenchymal imaging criteria; site investigators will determine if individual patients will benefit from thrombectomy. The trial is not intended to assess clinical criteria for endovascular treatment decisions, but rather to assess *technique* of thrombectomy once that decision has been made.

Inclusion criteria

1. Acute ischemic stroke due to occlusion of the terminal ICA or M1 segment of the MCA
2. Treatment can be initiated within 24 hours of onset
3. Age of 18 years or older

Exclusion criteria

Evidence of acute intracranial hemorrhage prior to treatment

Failure to obtain informed consent

Subject withdrawal

Subjects enrolled in the study can discontinue their participation at any time for any reason without prejudice or reduction in the quality of their medical care. The investigator can terminate a subject's participation in the study to protect the subject's health. The Investigator must document this notification of withdrawal from the study in the appropriate CRF and notify the sponsor.

Data collection

Baseline data: At the time of endovascular treatment, the following data will be collected for all subjects:

- Age
- Baseline mRS
- ASPECTS score
- Hyperdense vessel sign (yes/no; site-reported)
- NIHSS
- Location of occlusion (right or left, ICA terminus or M1)

Procedure data: The following will be collected immediately after the procedure:

- Guide catheter used
- Which Raptor used (0.071" or 0.074")
- Microcatheter used (Carrier or other)
- Microwire used
- Successful navigation? (yes/no)

- Total duration of aspiration
- Total duration of plunging (if assigned to Plunger technique)
- Reperfusion (TICI) after each pass (site-assessed)
- Clot ingestion: none, partial, or complete
- Groin puncture time
- On-clot time
- Time of reperfusion
- Rescue treatment? If yes, what device and how many passes

24 hour data: To be collected at 24 hrs post-procedure +/- 6 hours:

- Imaging evidence of hemorrhage? If parenchymal, HI1, HI2, PH1, or PH2; or IVH, SAH, SDH
- Symptomatic ICH?
- NIHSS

90 day follow up: To be collected by phone at 90 days +/- 30 days

- Modified Rankin Score

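### The 90-day mRS comparison names no covariates, although prior disability is not restricted and baseline mRS, age and NIHSS are already collected: a minor, nearly free gain in precision is left unclaimed

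*Protocol*

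**What the plan says.** Protocol, Analysis of secondary endpoints: "The 90-day functional outcomes, including mRS and PROMIS-10, will be compared between the two groups using ordinal shift analysis". No covariate is named, and the analysis is not called unadjusted either. The Secondary endpoints list gives the outcome as "Functional outcome at 90 days based on modified Rankin scale (mRS) assessment", with no effect size or power attached.

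Eligibility is broad. The inclusion criteria are the occlusion site, a 24-hour window and "Age of 18 years or older". The exclusions are "Evidence of acute intracranial hemorrhage prior to treatment" and lack of consent. Neither list limits disability before the stroke, and Patient selection leaves the rest to the sites: "Note that there are no parenchymal imaging criteria; site investigators will determine if individual patients will benefit from thrombectomy".

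Data collection lists age, baseline mRS, ASPECTS, hyperdense vessel sign, NIHSS and occlusion location, introduced by "At the time of endovascular treatment, the following data will be collected for all subjects". It does not say that baseline mRS means the score before the stroke. The Schedule of assessments confirms baseline mRS and NIHSS.

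The only covariates named for any analysis concern symptomatic hemorrhage: "Secondary analyses will account for ASPECTs score and time to treatment between the two groups". Randomization is 1:1 in permuted blocks, with no stratification factor named.

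**The concern.** A patient who was already disabled has little room to reach a good 90-day score in either arm. With no restriction at entry and no stratification factor named, baseline prognosis may vary widely between patients. If the ordinal model contains arm alone, that variation stays in the comparison as noise.

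Three things follow: the test is less powerful than the collected data allow, a chance difference between arms in prior disability or severity goes uncorrected in the estimate, and the common odds ratio lies closer to 1 than the one conditional on baseline. The Background justifies the trial partly by the expectation that more efficient reperfusion improves neurologic outcome. The 90-day mRS is the listed secondary endpoint that speaks to this, with PROMIS-10 beside it in the analysis, so its precision is worth having.

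**Working it through.** **The plan's own figure.** There is none for the mRS. The 462 in Sample size calculation belongs to the first-pass endpoint and is used here only as a number of patients.

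**Assumptions not in the protocol.** 462 evaluable patients; mRS 0–6 distributed 10/15/14/15/16/10/20%; proportional odds; two-sided 0.05; conditional common odds ratio 1.6; baseline covariates explaining 10%, 20% or 30% of latent variance.

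**Step 1: simulation at odds ratio 1.6** (1,500 trials per setting, error about 1 point). The mean unadjusted odds ratio comes from a separate repeat with 600 trials per setting.

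| Variance explained | Mean unadjusted OR | Power, unadjusted | Power, adjusted | Gain (points) |
|---|---|---|---|---|
| 10% | 1.56 | 76.7% | 81.1% | 4.4 |
| 20% | 1.51 | 70.5% | 82.7% | 12.2 |
| 30% | 1.44 | 62.4% | 79.6% | 17.2 |

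The repeat (error about 2 points) gave 79 vs 83%, 72 vs 81% and 61 vs 81%, gains of 4, 9 and 20 points.

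**Step 2: hand check of the unadjusted column.** The information on the log odds ratio is about N/12 × (1 − Σp³). Here Σp³ = 0.001 + 0.003375 + 0.002744 + 0.003375 + 0.004096 + 0.001 + 0.008 = 0.02359, so the information is 38.5 × 0.97641 = 37.59, with square root 6.131. Power is about Φ(6.131 × ln OR − 1.96):
- OR 1.56: Φ(2.726 − 1.96) = 78%
- OR 1.51: Φ(2.527 − 1.96) = 71%
- OR 1.44: Φ(2.236 − 1.96) = 61%

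These agree with the simulation.

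**Step 3: different assumptions.** With 450 patients, distribution 12/16/14/14/15/9/20%, odds ratio 1.5, and a prognostic index with SD 0.6, 1.0 or 1.4 on the logit scale, power was 62 vs 69%, 51 vs 67% and 42 vs 67% (1,000 trials per setting). Variance explained is SD²/(SD² + π²/3), so these SDs correspond to 10%, 23% and 37%.

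**Step 4: validity.** In the step 3 setting with odds ratio 1.0, rejection rates were 4.1–4.6% unadjusted and 4.7–5.6% adjusted. Both are near 5%.

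**Step 5: what effect is plausible?** Suppose the technique affects mRS only through first-pass success, at the protocol's rates of 25% and 40%, and that success multiplies the odds of a better score by f. Take a cut-point that half of the patients without success meet; those with success meet it with probability f/(1 + f). For f = 3 this is 75%:
- static: 0.75 × 0.50 + 0.25 × 0.75 = 0.5625
- Plunger: 0.60 × 0.50 + 0.40 × 0.75 = 0.6000
- odds ratio: (0.60/0.40)/(0.5625/0.4375) = 1.17

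For f = 2 the proportions are 0.5417 and 0.5667, giving 1.11. For f = 4 they are 0.575 and 0.620, giving 1.21. By the step 2 formula, adding the small opposite tail, power at 1.11, 1.17 and 1.21 is about 10%, 16% and 22%.

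Simulation at a conditional odds ratio of 1.15 (300 trials per setting, error about 2 points) gave 14 vs 16%, 11 vs 11% and 9 vs 14% for 10%, 20% and 30% of variance explained, gains of 2, 0 and 5 points.

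**The case against.** The strongest reply is that the covariate list for a secondary ordinal model is commonly left to the SAP, which is not at hand, and that an ordinal shift analysis may well be an adjusted proportional-odds model. This stands in part: a reader might infer that the protocol commits to a shift by arm alone, and the text does not establish that. Against it, the hemorrhage paragraph does name covariates, while the mRS sentence describes only a two-group comparison. If both readings are open, they lead to different odds ratios and different power, and one should be chosen before outcomes are seen.

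A reader might also infer bias, with old disability counted as a treatment effect. The design does not support that. Randomization balances prior disability in expectation, and the unadjusted test holds its error rate (step 4). Chance imbalance is covered by that rate over repeated trials; adjustment improves the estimate in the trial at hand. Nor is an odds ratio nearer 1 an error: marginal and conditional odds ratios are different quantities, and both are valid.

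The objection on size stands in full. An odds ratio of 1.6 is optimistic if the effect runs through first-pass success. Near 1.15 the endpoint is far underpowered with or without covariates.

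**Conclusion.** The point holds as a minor improvement. The protocol collects strong candidate predictors of 90-day mRS, admits patients regardless of prior disability, and names none of baseline mRS, age or NIHSS as a covariate in any analysis. An unadjusted analysis would be sound but less precise than it could be.

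The gain is roughly 4 to 20 points of power at a conditional odds ratio of 1.6 with 10–30% of latent variance explained, and about 0 to 5 points near 1.15. Both ranges rest on assumed effects, an assumed mRS distribution and assumed prognostic strength; the protocol supplies none of these. It would be wrong to conclude that adjustment rescues the endpoint, that the mRS is the only patient-level outcome (PROMIS-10 is analysed too), or that the trial's main result is at risk. The mRS is secondary and unpowered, and the first-pass comparison is unaffected.

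**What to change.** In Analysis of secondary endpoints, state that the main analysis of 90-day mRS is a proportional-odds model with arm, pre-stroke mRS, age and baseline NIHSS, reported as the adjusted common odds ratio with its 95% confidence interval. Keep the unadjusted shift as a supporting analysis.

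In Data collection, state that baseline mRS is the pre-stroke score. Without this, a score taken during the acute stroke would satisfy the text, and adjusting for it would not remove prior disability.

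The cost is a sentence in each place and no new data item. The odds ratio becomes conditional on the covariates and should be labelled so. The few patients with a missing baseline value need a simple fill-in rule so that they stay in the model.
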